8.2 End of study

The end of study is defined as 5 years after inclusion of the last patient.

9.0 ADVERSE EVENTS

An *Adverse Event (AE)* is defined as any new untoward medical occurrence or worsening of a preexisting medical condition in a clinical investigation subject administered study drug and that does not necessarily have a causal relationship with this treatment.

An AE can therefore be any unfavorable and unintended sign (such as an abnormal laboratory finding), symptom, or disease temporally associated with the use of study drug, whether or not considered related to the study drug.

The causal relationship to study drug is determined by a physician and should be used to assess all adverse events (AE). The causal relationship can be one of the following:

- Related: There is a reasonable causal relationship between study drug administration and the AE.
- Not related: There is not a reasonable causal relationship between study drug administration and the AE.

The term "reasonable causal relationship" means there is evidence to suggest a causal relationship.

Adverse events can be spontaneously reported or elicited during open-ended questioning, examination, or evaluation of a subject.

9.1 Management of adverse events

For recommendations on the management of adverse events, please see the last updated version of the Investigator's Brochure for nivolumab.

9.2 Serious Adverse Events

A *Serious Adverse Event (SAE)* is any untoward medical occurrence that at any dose:

- results in death
- is life-threatening (defined as an event in which the subject was at risk of death at the time of the event; it does not refer to an event which hypothetically might have caused death if it were more severe)
- requires inpatient hospitalization or causes prolongation of existing hospitalization (see **NOTE** below)
- results in persistent or significant disability/incapacity
- is a congenital anomaly/birth defect
- is an important medical event (defined as a medical event(s) that may not be immediately life-threatening or result in death or hospitalization but, based upon appropriate medical and scientific judgment, may jeopardize the subject or may require intervention [eg, medical, surgical] to prevent one of the other serious outcomes listed in the definition above). Examples of such events include, but are not limited to, intensive treatment in an emergency room or at home for allergic bronchospasm; blood dyscrasias or convulsions that do not result in hospitalization.) Potential drug induced liver injury (DILI) is also considered an important medical event. (See Section 8.7 for the definition of potential DILI.)

Suspected transmission of an infectious agent (eg, pathogenic or nonpathogenic) via the study drug is an SAE.

Although pregnancy, overdose, cancer, and potential drug induced liver injury (DILI) are not always serious by regulatory definition, these events must be handled as SAEs. (See Section 8 for reporting pregnancies).

Any component of a study endpoint that is considered related to study therapy (eg, death is an endpoint, if death occurred due to anaphylaxis, anaphylaxis must be reported) should be reported as SAE (see Section 8 for reporting details).

NOTE:

The following hospitalizations are not considered SAEs in this study:

- a visit to the emergency room or other hospital department < 24 hours, that does not result in admission (unless considered an important medical or life-threatening event)
- elective surgery, planned prior to signing consent
- admissions as per protocol for a planned medical/surgical procedure
- routine health assessment requiring admission for baseline/trending of health status (e.g., routine colonoscopy)
- medical/surgical admission other than to remedy ill health and planned prior to entry into the study. Appropriate documentation is required in these cases
- admission encountered for another life circumstance that carries no bearing on health status and requires no medical/surgical intervention (eg, lack of housing, economic inadequacy, caregiver respite, family circumstances, administrative reason).
- admission for administration of anticancer therapy in the absence of any other SAEs

9.2.1 Serious Adverse Event Collection and Reporting

The Investigator Brochure (IB) represents the Reference Safety Information to determine expectedness of serious adverse events for expedited reporting. Following the subject's written consent to participate in the study, all SAEs, whether related or not related to study drug, must be collected, including those thought to be associated with protocol-specified procedures. All SAEs must be collected that occur during the screening period and within 90 days of the last dose of nivolumab. If applicable, SAEs must be collected that relate to any later protocol-specified procedure (eg, a follow-up skin biopsy). For subjects included and never treated with study drug, SAEs should be collected for 30 days from the date of inclusion.

The investigator must report any SAE that occurs after these time periods and that is believed to be related to study drug or protocol-specified procedure.

An SAE report must be completed for any event where doubt exists regarding its seriousness.

If the investigator believes that an SAE is not related to study drug, but is potentially related to the conditions of the study (such as withdrawal of previous therapy or a complication of a study procedure), the relationship must be specified in the narrative section of the SAE Report Form.

SAEs, whether related or not related to study drug, and pregnancies, must be reported to Sponsor (or designee) within 24 hours of awareness of the event. SAEs must be recorded on the SAE Report Form; pregnancies on a Pregnancy Surveillance Form (electronic or paper forms).

If only limited information is initially available, follow-up reports are required.

If an ongoing SAE changes in its intensity or relationship to study drug or if new information becomes available, the SAE report must be updated and submitted within 24 hours to Sponsor (or designee) using the same procedure used for transmitting the initial SAE report.

All SAEs must be followed to resolution or stabilization.

9.3 Nonserious Adverse Events

9.3.1 Nonserious Adverse Event Collection and Reporting

The collection of nonserious AE information should begin at initiation of study drug until 90 days from the last dose of study drug.

Nonserious AEs should be followed to resolution or stabilization, or reported as SAEs if they become serious. Follow-up is also required for nonserious AEs that cause interruption or discontinuation of study drug and for those present at the end of study treatment as appropriate. All identified nonserious AEs must be recorded and described on the nonserious AE page of the CRF.

9.4 Laboratory Test Result Abnormalities

The following laboratory test result abnormalities should be captured on the nonserious AE CRF page or SAE Report Form as appropriate:

- Any laboratory test result that is clinically significant or meets the definition of an SAE
- Any laboratory test result abnormality that required the subject to have study drug discontinued or interrupted
- Any laboratory test result abnormality that required the subject to receive specific corrective therapy.

It is expected that wherever possible, the clinical rather than laboratory term would be used by the reporting investigator (eg, anemia versus low hemoglobin value).

9.5 Pregnancy

If, following initiation of the study drug, it is subsequently discovered that a study subject is pregnant or may have been pregnant at the time of study exposure, including during at least 5 half lives after product administration, the investigator must immediately notify the Sponsor of this event and complete and forward a Pregnancy Form to Sponsor within 24 hours of awareness of the event and in accordance with SAE reporting procedures.

In this case, the study drug will be permanently discontinued in an appropriate manner.

Follow-up information regarding the course of the pregnancy, including perinatal and neonatal outcome and, where applicable, offspring information must be reported on the Pregnancy Form.

Any pregnancy that occurs in a female partner of a male study participant should be reported to Sponsor. Information on this pregnancy will be collected on the Pregnancy Form.

9.6 Overdose

An overdose is defined as the accidental or intentional administration of any dose of a product that is considered both excessive and medically important. All occurrences of overdose must be reported as an SAE.

9.7 Potential Drug Induced Liver Injury (DILI)

Wherever possible, timely confirmation of initial liver-related laboratory abnormalities should occur prior to the reporting of a potential DILI event. All occurrences of potential DILIs, meeting the defined criteria, must be reported as SAEs.

Potential drug induced liver injury is defined as:

1. AT (ALT or AST) elevation > 3 times upper limit of normal (ULN)
AND
2. Total bilirubin > 2 times ULN, without initial findings of cholestasis (elevated serum alkaline phosphatase),
AND
3. No other immediately apparent possible causes of AT elevation and hyperbilirubinemia, including, but not limited to, viral hepatitis, pre-existing chronic or acute liver disease, or the administration of other drug(s) known to be hepatotoxic.

9.8 Dose Limited Toxicity (DLT)

We foresee that DLT related to Grade 3 and/or 4 dermatitis and mucositis may be experienced.

During dose escalation phase: If a patient experience a possibly nivolumab-related Grade 3 adverse event at any dose level, an additional patient will be included at this dose level. If one more patient experience the same Grade 3 event on the same dose level (i.e. 2 of 4 patients at one dose level experiences the same Grade 3 event), this will be defined as DLT reached, and the dose should be reduced by one level. If DLT is experienced at the lowest dose level (1,0 mg/kg), the dose will be reduced to 0.3 mg/kg. If two patients experience DLT at this dose level, the study will be terminated. If a patient experiences a Grade 4 event, the dose should immediately be reduced by one level.

The Safety Monitoring Committee (SMC) will meet in the case of DLT, to discuss further progress related to doses of nivolumab, and whether the protocol should be amended. In

addition, the SMC will meet after every time three patients have completed each dose level (i.e. completed the re-radiation), to discuss whether it will be safe to move to next dose level. No further patients will be included until the SMC has met. After the dose escalation phase has been completed, the SMC will meet if two patients experience AE grade 3 or one patient experiences AE Grade 4, considered related to nivolumab. No further patients will be included until the SMC has met.

The SMC is a group of oncologists located at the Clinical Cancer Research Unit, with experience in immunotherapy treatment. The members will not be involved in the study design or the study treatment.

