2.3 Rationale for Dose Selection

Nivolumab is safe and well tolerated up to 10 mg/kg Q2W dose level (see IB). The RT given in the present study gives considerable side effects, related to inflammation that may be enhanced by PD1 blockade. Nivolumab has shown efficacy and mild toxicity when given as monotherapy for HNSCC at a dose of 3.0 mg/kg Q2W, which is the target dose in the present trial(3). To assess the toxicity, the following dosing schedule has been chosen: Nivolumab, intravenous every 2nd week (1 cycle = 2 weeks), dose escalation schedule (1.0, 3.0 mg/kg), for a maximum of 12 months or until disease progression. RT will be given to a total dose of 60 Gy (1.5 Gy fractions twice daily) for a total period of 4 weeks. We expect that any increased toxicity will be observed within 2 weeks after end of RT and thus allow for a 3.0 mg/kg Q2W dose level thereafter. If a drug-related toxicity is observed, the guidelines outlined below will apply.

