3.0 SAFETY MONITORING COMMITTEE

A safety monitoring committee (SMC) will monitor safety on a periodic basis. Members of the

SMC will be experienced clinicians. The SMC will meet approximately every 6 months from the point of first patient in (FPI) to review safety and study conduct data. The safety data will include demographic data, adverse events and relevant laboratory data. In addition the SMC will meet after finalization of each dose cohort (i.e. three patients has completed minimum 8 weeks of treatment), and in case DLT is experienced. See section 8.8 for definitions.

Following each data review, the SMC will provide recommendations to the Study Leadership as to whether the study should continue or be amended, or whether the study should be stopped on the basis of safety (i.e., evidence of harm). The Study Leadership will make a decision on the basis of the SMC recommendations.

Any outcomes of these safety reviews that affect study conduct will be communicated in a timely manner to the investigators for notification of the Institutional Review Boards/Ethics Committees (IRBs/ECs).

No interim efficacy analysis is planned.

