5.2 Study treatment

The study will include 20 patients. The following treatment will be used:

- Radiotherapy (RT) to a total dose of 60 Gy, given as 1.5 Gy fractions twice daily for a total period of 4 weeks, will be delivered to the target volumes determined by PET-CT scan. Definition of target volumes and organs at risk will follow the Dahanca guidelines 2013 (published on www.dahanca.dk). The dose delivered to organs at risk, determined by PET-CT scan, will also be calculated.
- Nivolumab administered intravenous every two weeks, starting two weeks (Cycle 1, Day 1) before start of radiotherapy. Nivolumab will be given for a maximum of 12 months or until disease progression.
- Nivolumab will be administered according to a dose escalation schedule (1.0 and 3.0 mg/kg), as shown in Figure 1. Three patients will be included at each dose level. During the dose escalation part the subsequent patient will start therapy with nivolumab 6 weeks after the previous to allow time to observe the possibility for acute toxicity. If no dose limiting toxicity (DLT) is observed at the first dose level, additional three patients will be included at the next dose level. If DLT is experienced see section 8.8 for details. The remaining patients will be treated at the maximum tolerated dose.
- The nivolumab dose will be adjusted to 3.0 mg/kg (standard dose used in NCT02105636) for all patients from Cycle 5, Day 1 (2 weeks after end of radiotherapy), irrespective of starting dose.

The study treatment is outlined in Table 1. Trial treatment should begin within 28 days of first interventional screening assessments. Details on preparation and administration of nivolumab are provided in the IB.

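### The DLT rule in Section 9.8 sets no per-patient onset window although every patient moves to 3.0 mg/kg at week 8, and the two cohort review points disagree

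*Combined protocol and SAP*

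**What the plan says.** **The counting rule.** Section 9.8 (cited elsewhere in the protocol as 8.8) applies during dose escalation. After one "possibly nivolumab-related Grade 3 adverse event at any dose level, an additional patient will be included at this dose level". DLT is reached when "2 of 4 patients at one dose level experiences the same Grade 3 event", and the dose then drops one level. A single Grade 4 event also lowers the dose. None of these rules limits when in a patient's course the event must start.

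**The dose change.** Section 5.2 sets nivolumab to 3.0 mg/kg "for all patients from Cycle 5, Day 1 (2 weeks after end of radiotherapy), irrespective of starting dose". Section 2.3 gives the reason: the expectation that "any increased toxicity will be observed within 2 weeks after end of RT and thus allow for a 3.0 mg/kg Q2W dose level" from then on.

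**Staggered entry.** Each escalation level takes three patients, and "the subsequent patient will start therapy with nivolumab 6 weeks after the previous" (Section 5.2).

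**The cohort review.** Section 3.0 has the safety monitoring committee (SMC) meet once "three patients has completed minimum 8 weeks of treatment". Section 9.8 says that "the SMC will meet after every time three patients have completed each dose level (i.e. completed the re-radiation"), in order to judge whether moving up is safe.

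**The question to be answered.** The second primary objective in Section 4.1 is a safe nivolumab dose when given together with 60 Gy re-irradiation. Sections 6.1 and 11.1 plan descriptive adverse event summaries and do not mention a split by period or starting dose.

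**The concern.** The dose under test in the first cohort is 1.0 mg/kg with radiotherapy, and a patient in that cohort receives it only up to week 8. Suppose the first patient has a possibly related Grade 3 event at week 10. If dose level means starting dose, one patient is added at 1.0 mg/kg, although the most recent dose was 3.0 mg/kg. If it means current dose, the extra patient belongs to 3.0 mg/kg, a level that has not been opened and that this patient never received with radiotherapy. The two readings call for different actions, and the text does not choose between them.

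The review timing raises a separate problem. If the SMC meets when the third patient finishes radiotherapy, it can clear the next level before that patient has been observed in the two weeks after radiotherapy. Section 2.3 relies on those weeks.

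The counts at stake trigger the addition of patients and de-escalation, so they bear directly on the second primary objective.

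**Working it through.** **Inputs.** Two-week cycles, with radiotherapy in Cycles 2 and 3 for 4 weeks (Section 5.2.1, Table 1). 3.0 mg/kg from Cycle 5 Day 1, three patients per level and a 6-week stagger (Section 5.2). Review at 8 weeks (Section 3.0) or at the end of radiotherapy (Section 9.8). Assumption: no dose delays.

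**The plan's own timing.** Cycle 5 Day 1 is at (5 − 1) × 2 = week 8. Radiotherapy starts at week 2 and ends at week 2 + 4 = 6, and two weeks later is week 8. The statement in Section 5.2 is reproduced.

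**Review dates.** The first cohort starts at weeks 0, 6 and 12. The third patient ends radiotherapy at week 12 + 6 = 18 and reaches 8 weeks at week 12 + 8 = 20.

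**Time under observation at review.** At week 18 it is 18, 12 and 6 weeks for the three patients. At week 20 it is 20, 14 and 8 weeks. With no window, the three are counted over unequal periods.

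**Doses given before review.** Each patient has doses at own weeks 0, 2, 4 and 6 at 1.0 mg/kg, then every two weeks from own week 8 at 3.0 mg/kg.

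| Review | Patient 1 (1.0 + 3.0) | Patient 2 | Patient 3 | Total | Share at 3.0 mg/kg |
|---|---|---|---|---|---|
| Week 18 (Section 9.8) | 4 + 5 | 4 + 2 | 3 + 0 | 11 + 7 = 18 | 7/18 = 39% |
| Week 20 (Section 3.0) | 4 + 6 | 4 + 3 | 4 + 0 | 12 + 9 = 21 | 9/21 = 43% |

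Patient-weeks give the same shares: (10 + 4 + 0)/36 = 14/36 = 39% and (12 + 6 + 0)/42 = 18/42 = 43%.

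**With a window** from Cycle 1 Day 1 to before the Cycle 5 dose, and review at week 20, the cohort is judged on 3 × 8 = 24 patient-weeks and 12 doses, all at 1.0 mg/kg.

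**Review point against the rationale.** At week 18 the third patient has had 0 of the 2 post-radiotherapy weeks in Section 2.3. At week 20 that patient has had both.

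**The case against.** The strongest reply is that a window is already implied. Section 9.8 equates completing a dose level with completing re-irradiation, Section 3.0 treats a cohort as final after at least 8 weeks, and Section 2.3 gives the matching rationale. Much of this stands, and the fix probably states what the sponsor intended. But Sections 3.0 and 9.8 time committee meetings and disagree by two weeks, and Section 2.3 states an expectation. None of them says which events count.

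A second reply is that late events should count, because caution is proper in a first combination with re-irradiation. This stands in part. A reader might infer that events after Cycle 5 Day 1 say nothing about the dose given with radiotherapy. The documents do not support that: the half-life is up to 25 days (Section 5.1.1), and Section 2.1 notes late as well as acute toxicity after re-irradiation. Such events reflect mixed exposure and must stay visible.

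Third, the shares do not measure an effect on the decision. This also stands. The 2-of-4 rule needs the same event twice, and Section 9.8 names dermatitis and mucositis as the events foreseen. A larger share could be computed for a cohort extended to four patients. It would assume on-time dosing after a Grade 3 event, whereas Sections 5.3.2.1 and 5.3.2.3 often require delay or discontinuation.

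Finally, the SMC meets at any DLT and can weigh onset and current dose. This is a real safeguard, but the committee has no stated attribution rule.

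**Conclusion.** The concern holds as a gap in the counting rule and a conflict between two stated review points, and it should be fixed. Up to 39% to 43% of first-cohort doses before review are not the dose under test. This assumes the 6-week stagger, no delays and the text alone, since Figure 1 was not available. The plan gives no Grade 3 rates by period for the combination, so no probability of a wrong dose decision follows. If no patients are added under the DLT rule, the dose changes at week 8 for only 3 of 20 patients, but those three decide escalation. For patients who start at 3.0 mg/kg, the missing window is a matter of timing only.

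Three stronger readings should not be drawn:

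- A reader might infer that the gap could readily end the trial, because of "If two patients experience DLT at this dose level, the study will be terminated". That needs DLT at 1.0 mg/kg, reduction to 0.3 mg/kg and two further patients with DLT, with the SMC meeting at DLT. It is remote.
- A reader might see an error in raising patients to 3.0 mg/kg at week 8 after they start at a level lowered for DLT. That follows from Section 2.3 and is a design choice.
- A reader might take Sections 6.1 and 11.1 to prescribe pooled adverse event tables. They are silent on a split, and one can still be made at reporting.

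**What to change.** - **Section 9.8, counting.** Count an event towards the DLT rule for the patient's starting dose level if its onset is from Cycle 1 Day 1 to before the Cycle 5 Day 1 dose. Say what closes the window if that dose is delayed or not given.
- **Sections 3.0 and 9.8, review.** Set the cohort SMC review in both places at 8 weeks for the last patient in the cohort.
- **Later events.** Give the SMC a separate listing of possibly related Grade 3-4 events from Cycle 5 Day 1 onwards, on which it may act, because delayed effects of Cycle 1-4 treatment can appear there. The individual discontinuation rules in Section 5.3.2.3 do not change.
- **Optional, Section 11.1.** Tabulate adverse events before and from Cycle 5 Day 1 by starting dose.

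The cost is a few protocol sentences and, if the option is taken, one table split from data already collected. Moving the Section 9.8 review from week 6 to week 8 adds about two weeks per cohort. The downside is that delayed events caused by treatment in Cycles 1-4 fall outside the formal count, which is why the separate listing is needed.

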5.3.2 Dose Modifications for Nivolumab

Dose modification is only allowed in case of Dose Limited Toxicity (DLT). See section 8.8 for instructions. For dose delay, see 5.3.2.1

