5.3.2.3 Treatment Discontinuation Criteria for Nivolumab

Nivolumab treatment should be permanently discontinued for the following:

- Any grade 4 drug-related toxicity
- Any Grade 2 drug-related uveitis, eye pain or blurred vision that does not respond to topical therapy and does not improve to Grade 1 severity within the re-treatment period OR requires systemic treatment.
- Any Grade 3 non-skin, drug-related adverse event lasting > 7 days, with the following exceptions for laboratory abnormalities, drug-related uveitis, pneumonitis, bronchospasm, hypersensitivity reactions, infusion reactions, and endocrinopathies:
 - Grade 3 drug-related uveitis, pneumonitis, bronchospasm, hypersensitivity reaction, or infusion reaction of any duration requires discontinuation
 - Grade 3 drug-related endocrinopathies adequately controlled with only physiologic hormone replacement do not require discontinuation
 - Grade 3 drug-related laboratory abnormalities do not require treatment discontinuation except:
 - Grade 3 drug-related thrombocytopenia > 7 days or associated with bleeding requires discontinuation
- Any drug-related liver function test (LFT) abnormality that meets the following criteria require discontinuation:
 - AST or ALT > 5 x ULN for 2 weeks
 - AST or ALT > 5 x ULN
 - Total bilirubin > 3 x ULN
- Any Grade 4 drug-related adverse event or laboratory abnormality, except for the following events which do not require discontinuation:
 - Grade 4 neutropenia ≤ 7 days
 - Grade 4 lymphopenia or leukopenia
 - Isolated Grade 4 amylase or lipase abnormalities that is not associated with symptoms or clinical manifestations of pancreatitis. The Study leadership should be consulted for Grade 4 amylase or lipase abnormalities.
 - Isolated Grade 4 electrolyte imbalances/abnormalities that are not associated with clinical sequelae and are corrected with supplementation/appropriate management within 72 hours of their onset
 - Grade 4 drug-related endocrinopathy adverse events, such as adrenal insufficiency, ACTH deficiency, hyper- or hypothyroidism, or glucose intolerance, which resolve or are adequately controlled with physiologic hormone replacement (corticosteroids, thyroid hormones) or glucose-controlling agents, respectively, may not require discontinuation after discussion with and approval from the Study leadership.
- Any event that leads to delay in dosing lasting > 6 weeks from the previous dose requires discontinuation, with the following exceptions:

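### Section 5.3.2.3 gives opposite instructions for some drug-related Grade 4 events, and the escalation-phase Grade 4 rule in section 9.8 leaves relatedness, exceptions, scope and DLT status unstated

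*Combined protocol and SAP*

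**What the plan says.** Section 5.3.2.3 opens its list with "Nivolumab treatment should be permanently discontinued for the following". Two bullets of that list deal with Grade 4 events in general:

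- The first bullet reads "Any grade 4 drug-related toxicity" and carries no exception.
- A later bullet reads "Any Grade 4 drug-related adverse event or laboratory abnormality, except for the following events which do not require discontinuation". The exceptions are short-lived neutropenia, "Grade 4 lymphopenia or leukopenia", isolated amylase or lipase abnormalities without pancreatitis, isolated electrolyte abnormalities that are corrected in time, and controlled endocrinopathies (these last subject to approval by the study leadership).

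Section 5.5 makes an adverse event described in 5.3.2.3 a mandatory reason for discontinuation.

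Section 9.8, in the paragraph on the escalation phase, says: "If a patient experiences a Grade 4 event, the dose should immediately be reduced by one level". Two neighbouring rules in that section are worded differently. The Grade 3 rule begins "If a patient experience a possibly nivolumab-related Grade 3 adverse event at any dose level". The trigger for a meeting of the safety monitoring committee (SMC) after escalation is that "one patient experiences AE Grade 4, considered related to nivolumab", or that two patients have a related Grade 3 event.

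Section 5.3.2 permits a change of nivolumab dose only for a DLT and refers to the DLT section for instructions. It cites that section as 8.8; the section is now numbered 9.8. This is a numbering slip and plays no part in the point.

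**The concern.** There are two separate problems.

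The first lies inside section 5.3.2.3 and applies in every phase. For any event on the exception list, two bullets of one list give opposite answers on whether the patient must stop for good. Nothing says which bullet prevails.

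The second concerns escalation only. The Grade 4 sentence in 9.8 leaves out the elements needed to apply it: which events count, and on whom the reduction acts. Finding a safe nivolumab dose is the second primary objective (section 4.1), and section 5.2 treats the remaining patients at the maximum tolerated dose. If each of the two planned levels takes exactly three patients, that is 20 − (3 + 3) = 14 of the 20. Two investigators who see the same Grade 4 event could in good faith reach different dose levels.

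**Working it through.** The plan states no figure on this point, and none is needed. The check is to take four Grade 4 events and read each rule literally.

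| Event | 5.3.2.3, first bullet | 5.3.2.3, later bullet | 9.8 |
|---|---|---|---|
| A. Drug-related lymphopenia, escalation | Stop permanently | Stop not required | One-level reduction; patient or level not stated |
| B. Drug-related, not on the exception list, escalation | Stop permanently | Stop permanently | One-level reduction; patient or level not stated |
| C. Judged unrelated to nivolumab, escalation | Does not apply | Does not apply | Literally, one-level reduction; none if relatedness is implied |
| D. Drug-related lymphopenia, after escalation | Stop permanently | Stop not required | No reduction rule; SMC meets and inclusion pauses |

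1. **Rows A and D.** The two bullets disagree whatever is made of 9.8. The clash is between bullets of one section and does not depend on the phase.

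2. **Row B.** The bullets agree. Whether 9.8 agrees with them depends on whose dose is meant. If it is the level for later patients, the affected patient stops and the next ones start lower, and both rules can be followed. If it is the affected patient's own dose, a patient who has stopped cannot also be reduced. The surrounding sentences in 9.8 speak of dose levels, which points to the first reading. Section 5.3.2 stands among the rules for dosing an individual patient and sends the reader to the DLT section, which points to the second. On that second reading, section 5.2 also moves every patient to 3.0 mg/kg from Cycle 5 without saying whether a reduced patient is included.

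3. **Row C.** This is a realistic case. Section 2.1 expects serious acute toxicity from re-irradiation itself, and 9.8 foresees dermatitis and mucositis of Grade 3 or 4. If such an event is attributed to radiotherapy alone, the Grade 4 bullets of 5.3.2.3 are silent, while 9.8 read literally lowers the dose.

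4. **DLT status.** Section 9.8 declares DLT reached when two of four patients at a level have the same Grade 3 event. It does not say whether one Grade 4 event is a DLT. Two things depend on this: section 5.3.2 allows dose modification only for a DLT, and sections 3.0 and 9.8 convene the SMC when a DLT occurs. After escalation, one related Grade 4 event expressly triggers a meeting and a pause in inclusion. During escalation that consequence rests on the undefined status.

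**The case against.** **The rules work at different levels.** Section 5.3.2.3 governs whether a patient stays on nivolumab; the 9.8 paragraph governs escalation. A reader might infer a direct three-way contradiction between stopping, stopping with exceptions, and reducing. The documents do not support that. The 9.8 sentence is confined to escalation, and read at cohort level it can coexist with stopping the affected patient. This part of the objection stands. It does not settle the matter, because the text does not state the cohort reading, excepted and unrelated events stay open under it, and it leaves the clash inside 5.3.2.3 untouched.

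**Relatedness is implied.** A reader might infer that 9.8 lowers the dose whatever the cause. That is only the literal reading. The sentence stands under a toxicity heading, between two rules that require relatedness, so the omission may be a slip. It is still an omission in a rule that one event can trigger.

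**A Grade 4 event may well be a DLT.** A reader might infer from the two-of-four wording that one Grade 4 event is not a DLT, so that 5.3.2 forbids what 9.8 orders. The documents do not establish this. Section 9.8 foresees DLTs of Grade 4, and its sentence on the 0.3 mg/kg level speaks of two patients each having a DLT. The status is unclear; it is not settled either way.

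**The first bullet may not cover laboratory findings.** If toxicity meant clinical events only, most exceptions would fall outside it. But section 8.1.2.1 itself speaks of laboratory toxicities, and the endocrinopathy exception concerns adverse events, so a clash would remain.

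**There are safeguards.** The SMC discusses doses after a DLT and after each completed level, and the study leadership is consulted on some Grade 4 exceptions. The safe-dose conclusion therefore does not turn mechanically on the wording. The safeguards do not reconcile the text, and during escalation the SMC trigger depends on the undefined DLT status.

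**Conclusion.** The point holds in two parts. First, section 5.3.2.3 contradicts itself for every drug-related Grade 4 event on its exception list, in all phases. This needs no assumption beyond reading the two bullets as written. Second, the escalation-phase Grade 4 rule in 9.8 is incomplete: relatedness, the exceptions, its scope and the DLT status of a single event are all unstated, so the dose-level decision can differ by reader. This is ambiguity and not proven conflict, because a cohort-level reading lets 9.8 stand beside 5.3.2.3 for events that both cover.

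No numerical size is given. The documents state no Grade 4 rate for nivolumab with re-irradiation. The chance of any Grade 4 event in a cohort, at an assumed rate, would not measure how often the readings disagree. The matter deserves correction because it bears on patient safety and on a primary objective.

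**What to change.** Reconcile the two Grade 4 bullets in 5.3.2.3 with each other and with 5.3.2 and 9.8, so that the protocol states one consistent Grade 4 rule and says:

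- which drug-related Grade 4 events require permanent discontinuation;
- whether the 9.8 reduction requires relatedness to nivolumab, and in what terms;
- whether the 5.3.2.3 exceptions apply during escalation;
- whether the reduction acts on the affected patient, on the dose level for later patients, or on both, and, if on the patient, how that fits the Cycle 5 dose in section 5.2;
- whether one Grade 4 event is a DLT, and hence whether it convenes the SMC during escalation.

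The choice among the clinical rules belongs to the sponsor and the SMC; this review takes no position on it. The cost is protocol wording only. Sample size, visits and data collection do not change.
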